9.1.5 Unsolicited Adverse Event

Unsolicited AEs are defined as any AEs reported spontaneously by the participant, observed by the study staff during study visits or those identified during review of medical records or source documents. Solicited AEs with an onset after the 7-day solicitation period (day 1-7) will be considered unsolicited AEs. An unsolicited AE is defined as any AE that is volunteered from the participant and occurs within 28 days after vaccination (day 1-28).

The percentage of participants with unsolicited AEs onset date within day 1-28 will be provided by age group, dose group, by grade, outcome and causality (any, fatal, causally related, fatal/causally related).

The number and percentage of participants with unsolicited AEs onset date within day 1-28 will be provided by SOC and PT for each dose group (any grade, grade 3, related).

Unsolicited AEs will be summarized and listed up to day 28 after study vaccination (day 1-28).

A data listing for all Unsolicited AEs will be provided by age group, dose group and participant number.

9.1.6 Adverse Events of Special Interest

An AESI (serious or nonserious) is defined as an AE or SAE of scientific and medical concern specific to the sponsor's product or program, for which ongoing monitoring and rapid communication by the investigator to the sponsor could be appropriate (ICH E2F; CIOMS VI).

Adverse events of special interest will include the following events:

- Virologically confirmed Covid-19 (see protocol section 6.4 for definitions)

- Potential immune-mediated disorders (see protocol section 13.4 for definitions)
- Anaphylaxis or severe hypersensitivity within 24 hours after study vaccine administration
- Myocarditis
- Pericarditis

AESIs will be identified using MedDRA queries and Investigator identification as per eCRF. Refer to appendix [15.3. MedDRA queries for identifying AESIs](#) for details on these queries.

The percentage of participants with AESIs with onset date within day 1-28 and within day 1-180, identified by either the investigator or by MedDRA queries, will be provided by SOC and PT for each dose group.

Similarly, AESIs that are related to COVID-19 will be presented in a separate listing by age group, dose group and participant number.

AESIs will be reported until exit from study (up to day 180 after the study vaccine administration, day 1-180).

9.1.7 Serious Adverse Events

An SAE is defined as any event that:

- Results in death
- Is immediately life-threatening
- Requires inpatient hospitalization or prolongation of existing hospitalization
- Results in persistent or significant disability/incapacity
- Is a congenital anomaly/birth defect
- Is an important medical event that may not result in death, be life-threatening, or require hospitalization but, based upon appropriate medical judgment, jeopardizes the participant or may require medical or surgical intervention to prevent one of the other outcomes listed in this definition. Examples of such medical events include allergic bronchospasm requiring intensive treatment in an emergency room or at home, blood dyscrasias or convulsions that do not result in inpatient hospitalization, or the development of drug dependency or drug abuse. All events of myocarditis and pericarditis will be considered important medical events and SAEs (see protocol section 6.1.3).

The percentage of participants with SAEs onset date within day 1-180 will be provided by dose group, by grade, outcome and causality.

The number and percentage of participants with SAE onset date within day 1-28 and within day 1-180 will be summarized by SOC, PT and causality for each dose group (any, fatal, causally related, fatal/causally related).

SAEs will be summarized and listed from the time participant signs the ICF until exit from study (up to day 180 after the study vaccine administration, day 1-180).

A data listing for all SAEs will be provided by age group, dose group and participant number.

9.1.8 Medically Attended Adverse Events

Medically attended adverse events (MAAEs) is defined as an AE that results in a visit to a medical professional (eg, telephone call, physician's office visit, urgent care visit, emergency room visit or hospitalization). Scheduled study visits will not be considered medically attended visits. Medically attended adverse events related to study vaccination are to be reported from the time of first study vaccination until completion of the participant's last study-related procedure, which may include contact for safety follow-up.

The percentage of participants with MAAE onset date within day 1-180 will be provided by dose group and by grade.

All MAAEs and treatment-related MAAEs with onset date within day 1-28 and within day 1-180 will be presented in separate summary tables for each dose and age group and total by SOC and PT. All MAAEs will be presented in a data listing by age group, dose group and participant number.

MAAEs will be reported in both listings and summaries from the time participant signs the ICF until exit from study (up to day 180 after the study vaccine administration, day 1-180).

9.1.9 Adverse Events Leading to Treatment Discontinuation

Not applicable.

9.1.10 Adverse Events Leading to Study Discontinuation

Adverse events leading to study discontinuation are identified on the study disposition page of the eCRF by the AE number.

The number and percentage of participants with AE leading to discontinuation with onset date within day 1-28 will be summarized by SOC and PT for each dose group.

AEs leading to study discontinuation will be presented and a data listing will be provided by age group, dose group and participant number.

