### 3 Investigational Plan – Study Design

This open-label, dose escalation FTiH Phase 1 study will evaluate the safety (including reactogenicity) and immunogenicity of a single booster dose of CV0501 vaccine in adults who have previously received at least 2 doses of an mRNA COVID-19 vaccine ([Section 4.1.1](#)). Approximately 180 participants will be enrolled. The study will comprise two parts (Part A and Part B).

The study duration per participant will be approximately 194 days from start of screening through EOS, including approximately 14 days for screening and approximately 180 days (6 months) for Day 1 vaccination and follow-up. There will be 6 protocol-scheduled visits: on Day 1 (vaccination day) and on Days 8, 15, 29, 91 and 181. In addition, there will be one protocol-scheduled telephone contact on Day 4 to query participants about solicited and unsolicited AEs occurring after study vaccination.

CCI

Participants will be monitored for potential COVID-19 illness from Day 1 through the EOS (Day 181). Participants will be asked to contact the site if they experience any symptoms of COVID-19 and will also be asked to report any positive SARS-CoV-2 diagnostic test.

Participants will also be required to document all AE symptoms and contact the site if necessary. An unscheduled visit may also be performed if an AE requires further evaluation.

Safety data will be monitored on an ongoing basis by the investigator (or medically qualified designee) and sponsor to promptly identify and flag any event that potentially could trigger a stopping rule. If a stopping rule is triggered, study intervention administration and enrollment will pause and the SRT will review available safety data from all vaccinated participants. Participants who have already received vaccine will continue to attend follow-up visits as specified in the schedule of events ([Table 13-1](#)). There are 2 planned interim analyses of safety and immunogenicity data ([Section 7.7](#)).

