## **4.2 Discontinuation From Study Intervention and/or Withdrawal From the Study**

As this is a single-dose study, discontinuation from study intervention does not apply.

Individual participants may withdraw from the study at any time at their own request for any reason without prejudice to their future medical care by the investigator or at the study site. The reasons for participants withdrawing from the study will be recorded in the eCRF.

Participants will be informed of any new authorized or licensed booster vaccines that become available for prevention of COVID-19 during the study to support an informed choice for whether to continue or discontinue participation in the study.

A participant may withdraw or be withdrawn from the study for any of the following reasons:

- Participant request.
- Investigator request.
- The participant is noncompliant with the protocol.

- The participant has a serious or intolerable AE(s) that, in the investigator's opinion, requires withdrawal from the study.
- The participant is lost to follow-up.
- Death.
- The sponsor terminates the study.

If a participant withdraws or is withdrawn from the study, ET procedures should be completed as indicated in the SOE ([Table 13-1](#)). Every effort will be made to continue to monitor the safety of participants who received a dose of IP and are withdrawn from the study.

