5.1. Disposition

Participant disposition will be summarized by dose group for all participants. The number and percentage of participants for the following categories will be presented: participants who were enrolled, vaccinated, participants who discontinued from the study (i.e. did not complete the day 181 visit), participants in the Enrolled Set, PPI Set and Safety Set.

A participant may withdraw or be withdrawn from the study for any of the following reasons:

- Participant request.
- Investigator request.
- The participant is noncompliant with the protocol.
- The participant has a serious or intolerable AE(s) that, in the investigator's opinion, requires withdrawal from the study.
- The participant is lost to follow-up.

- Death.
- The sponsor terminates the study.
- The participant has safety laboratory results that reveal clinically significant hematological or biochemical changes from the baseline values, per investigator judgment
- The participant has symptoms or an intercurrent illness not consistent with the protocol requirements or that justify withdrawal
- Other reasons (e.g., pregnancy, development of contraindications of use of the IP)
- The participant withdraws consent, or the investigator or sponsor decides to discontinue their participation in the study withdrawal of consent by participant or the investigator or sponsor decides to discontinue their participation in the study

Participant status summary will also be provided which include participants who completed each visit, participants vaccinated with study vaccine, participants who had immunogenicity results at applicable visit, and participants who completed the study. Participant status summary will be also presented by dose and age group.

Participant disposition and discontinuation data will be presented in a listing sorted by age, dose group and participant number.

The number of participants included in each analysis set will be summarized. A listing of participants in each analysis set will also be provided by age, dose group and participant number. Participants excluded from the analysis sets will be listed with reason for exclusion(s) and sorted by age, dose group and participant number.

The primary reason for study discontinuation includes: Withdrawal due to AE, Lost To Follow-up, Physician Decision, Pregnancy, Site Terminated by Sponsor, Study Terminated by Sponsor, Withdrawal of Consent by Participant, Protocol Deviation, Vaccine Not Administered, Death, Other.

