9.1.11 Death

The summary of AEs with an outcome of "Fatal" with onset date within day 1-180 will also be presented by SOC. The SOCs will presented alphabetically. Within each SOC, the PTs will be presented in alphabetical order.

All participants who have an AE with an outcome of "Death" will be presented in a listing by age group, dose group and participant number.

Deaths will be reported for both summaries and listings from the time participant signs the ICF until exit from study (up to day 180 after the study vaccine administration, day 1-180).

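### SAP 9.1.10 tabulates adverse events leading to study discontinuation only for onset in Day 1-28, so the per-dose table is incomplete for a study followed to Day 181

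*SAP*

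**What the plan says.** SAP 9.1.10 identifies these events through the AE number on the eCRF study disposition page and defines a single summary by SOC and PT for each dose group: "The number and percentage of participants with AE leading to discontinuation with onset date within day 1-28 will be summarized". The same section adds, without an onset limit, that "AEs leading to study discontinuation will be presented and a data listing will be provided by age group, dose group and participant number".

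Discontinuation is a whole-study outcome elsewhere in the plan:

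- SAP 5.1 counts "participants who discontinued from the study (i.e. did not complete the day 181 visit").
- SAP 5.1 also lists the reasons, with no time limit: "The primary reason for study discontinuation includes: Withdrawal due to AE, Lost To Follow-up", followed by others.
- Protocol 4.2 permits withdrawal when "The participant has a serious or intolerable AE(s) that, in the investigator's opinion, requires withdrawal from the study", again without a time limit.
- Protocol section 3 plans "approximately 180 days (6 months) for Day 1 vaccination and follow-up".

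**The concern.** The Day 1-28 limit is the window for unsolicited AEs (SAP section 4 and 9.1.5). It may have been carried into 9.1.10 from there, although the SAP gives no reason and this is inference. It does not fit an outcome that can occur until Day 181 and can be caused by events that are still being collected.

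SAP section 9 names AEs leading to withdrawal from study participation as one of the parameters by which safety, tolerability and reactogenicity are assessed, with no Day 28 limit. Someone reading the 9.1.10 table as the study's count of AE-driven withdrawals at each dose would get a count that stops early. The events it can miss are late SAEs, MAAEs and AESIs, for example an immune-mediated disease starting on Day 60.

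**Working it through.** There is no stated figure to reproduce: the point is about a reporting window, and the study has no hypothesis testing (protocol 7.1).

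**Step 1. Which events can be recorded after Day 28?** Under protocol 6.1.1.2, nonserious AEs are reported until 28 days after vaccination. Under footnote j of the Schedule of Events, SAEs, MAAEs and AESIs are collected throughout the study. A late AE that leads to withdrawal will therefore normally be one of those three types.

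**Step 2. Onset windows of the planned summaries.**

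| SAP section | Events | Onset windows summarised |
|---|---|---|
| 9.1.6 | AESIs | Day 1-28 and Day 1-180 |
| 9.1.7 | SAEs | Day 1-28 and Day 1-180 |
| 9.1.8 | MAAEs | Day 1-28 and Day 1-180 |
| 9.1.11 | Fatal AEs | Day 1-180 |
| 9.1.10 | AEs leading to study discontinuation | Day 1-28 only |

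Among these five, only 9.1.10 lacks a summary to Day 180.

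**Step 3. Trace three cases.**

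- SAE with onset on Day 60, participant withdrawn because of it: counted in the Day 1-180 SAE table, present in the 9.1.10 listing, absent from the 9.1.10 table.
- AE with onset on Day 20, participant withdrawn on Day 100: counted in the 9.1.10 table, because the limit is on onset and not on withdrawal date.
- Fatal AE with onset on Day 60: counted in the 9.1.11 table. It could not enter the 9.1.10 table as written, even if the disposition page links it to discontinuation.

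**Step 4. Length of the gap.** Days 29 to 180 are 180 − 28 = 152 days. 152/180 = 84.4% of the follow-up days, and 152/30.4375 = 4.99 months. Counting to Day 181 gives 153/181 = 84.5%. SAP section 4 describes the unsolicited window as the vaccination day plus 28 further days but labels it Day 1 through 28. If the window closes on Day 29, the gap is 151/180 = 83.9%. The conclusion is the same in each case.

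**Step 5. Weight of one case.** In a Part A cohort of 30, 1/30 = 3.3 percentage points. In a Part B cohort of 15, 1/15 = 6.7. If the table were also split by age, at the minimum of 10 per age group, 1/10 = 10. These figures only show the scale of a single hypothetical case.

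**Step 6. Expected number missed.** This cannot be derived. It needs a rate of AE-driven withdrawal and a distribution of onset times, and the documents give neither. Assuming onset spread evenly over 180 days would be hard to defend, because fewer types of event are collected after Day 28.

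**The case against.** The case for leaving the SAP alone has real substance.

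- **The events are not lost.** A reader might infer that only a listing would reveal a late case. The documents do not support that: late SAEs, MAAEs, AESIs and deaths each have a Day 1-180 summary. What those tables lack, as described, is any mark that the event led to withdrawal. This part of the objection stands.
- **The table is not wrong on its own terms.** A table defined by Day 1-28 onset counts Day 1-28 onset correctly, and Day 1-28 is the only period in which every type of AE is collected. This also stands. The fault is incompleteness for the whole study.
- **The sentence about presenting these AEs has no window.** It might be read as promising an unrestricted summary, but it defines no table beyond the listing. It secures the listing and leaves the summary unchanged.
- **The consequences are limited.** AEs leading to discontinuation are not a primary or secondary endpoint. This is a single-dose study, so discontinuation of treatment does not apply. Escalation uses data up to Day 8 (protocol 3.1.1) and the interim analyses follow Day 15 visits (protocol 7.7). With about 180 open-label participants, cases can be read one by one in the listing. All of this lowers the stakes, but it gives no reason for this section to differ from those around it.

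**Conclusion.** The point holds as a completeness gap. As written, the only per-dose SOC and PT summary of AEs leading to study discontinuation leaves out any such event with onset on Days 29-180, although the plan collects those events and tabulates them to Day 180 under other headings. It changes no primary endpoint and no dose decision within the study.

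Two stronger conclusions should be avoided. The 84.4% is a share of onset time and must not be read as the share of AE-driven withdrawals missed. Nor should the table be expected to equal the number recorded as withdrawn because of an AE. SAP 5.1 records one primary reason per participant and keeps death, pregnancy, physician decision and withdrawal of consent as separate categories, so a participant with a contributing AE may be coded elsewhere. SAP 5.1 also does not expressly say that the reasons are tabulated by dose group, so a mismatch between two tables is an inference.

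The conclusion rests on reading the onset limit literally and on there being no second table in the output shells, which are not among the documents.

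**What to change.** In SAP 9.1.10, summarise AEs leading to study discontinuation by SOC and PT for each dose group for onset within Day 1-28 and for onset within Day 1-180 (vaccination to end of study), as 9.1.6 to 9.1.8 already do for their events. Keep the listing unrestricted by onset.

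Add a cross-check against the discontinuation reasons recorded under SAP 5.1, with any differences explained and no requirement that the totals be equal.

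The cost is one SAP sentence and one extra table column. No new data are needed, because the AE number is already on the eCRF disposition page.

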9.1.11 Death

The summary of AEs with an outcome of "Fatal" with onset date within day 1-180 will also be presented by SOC. The SOCs will presented alphabetically. Within each SOC, the PTs will be presented in alphabetical order.

All participants who have an AE with an outcome of "Death" will be presented in a listing by age group, dose group and participant number.

Deaths will be reported for both summaries and listings from the time participant signs the ICF until exit from study (up to day 180 after the study vaccine administration, day 1-180).

9.2 Clinical Laboratory Evaluations

The following laboratory assessments will be performed:

Hematology:	Basophils, eosinophils, erythrocytes (red blood cells), hemoglobin, leukocytes (white blood cells), lymphocytes, monocytes, neutrophils, and platelets
Chemistry:	Alanine aminotransferase, alkaline phosphatase, aspartate aminotransferase, total and direct bilirubin, blood urea nitrogen, and creatinine
SARS-CoV-2:	
 SARS-CoV-2 serology (antibody) will include N protein for prevaccination and postvaccination timepoints. SARS-CoV-2 RT-PCR (nasopharyngeal or mid-turbinate swab)
HIV/HBV/HCV	
 Hepatitis B surface antigen test HIV 4th generation antigen/Ab test Anti-HCV Ab test (and RNA test if anti-HCV Ab positive)
Other analyses:	
Female participants of childbearing potential:
 
 β-human chorionic gonadotropin (serum test at screening; urine test at additional time points) Serum FSH, to confirm postmenopausal status

Individual safety laboratory measurements for hematology, chemistry and coagulation laboratory panel will be provided. All listings will include the cohort, study vaccine, participants ID, laboratory test name result, date and time of measurements, reference range, and flag for measurements that are outside the reference range and sorted by age group, dose group and participant number.

Laboratory abnormalities will be graded for severity using the FDA toxicity grading table (DHHS 2007). Clinically relevant laboratory abnormalities will be reported as AEs using the AE grading.

A summary of patients with an abnormal laboratory value after study vacation (up to Day 8) will be presented. An abnormal laboratory is defined as any value outside of the normal range.

A by-participant listing will be provided for pregnancy test by age group, dose group and participant number.

